2.2 Secondary Outcomes

- Endocrine toxicity and tolerability measured by the change in total score and individual items of FACT-ES from baseline to 4, 8, 12 and 52 weeks following the beginning of endocrine therapy
- Quality of life measured by the change in the total score and individual subscales of the validated Functional Assessment of Cancer Therapy for patients with a Breast cancer (FACT-B) questionnaire from baseline to 4, 8, 12 and 52 weeks following the beginning of endocrine therapy
- Rates of discontinuation, interruption and non-compliance (defined as patient taking less than 80% of the prescribed endocrine therapy) with initially prescribed endocrine therapy
- Cost-effectiveness: incremental cost-effectiveness ratios (cost per one quality-adjusted life year (QALY) gained

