5.1 Sample size

Our primary outcome is the change in total FACT-ES score from baseline to 12 weeks following the beginning of endocrine therapy.

Based on Fallowfield et al., a clinically meaningful effect would be observed if the change exceeded 0.5 of the standard deviation at baseline and the standard deviation at baseline is approximately 8.5²⁵. Therefore a ‘clinically meaningful change’ from baseline to 12 weeks would be a change of 4.25 or greater. It is also assumed that 40% of patients will experience a clinically meaningful change, and prescribing the time of day for administration of treatment would be important if there was an actual difference in clinically meaningful change rates of 20% or more (i.e. 40% with a clinically meaningful change in one arm and 60% in the other). Therefore, based on these assumptions and using a two-sided, alpha=0.05 Fisher’s exact test, we would need 214 total patients to achieve 80% statistical power. To account for potential loss to follow-up, and to account for stratification factors, the target sample size will be inflated by 10% to a total of 235.

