5.2 Analysis Methods

Descriptive analysis: Baseline characteristics will be presented with means (continuous measures) or proportions (categorical or ordinal data) with 95% confidence intervals.

Intention-to-treat analysis: The primary analysis will be based on the intent-to-treat principle, thus, all participants who are randomized will be included in the final study analysis. The last observation carried forward method will be used to impute results for any patient who is lost to follow-up, or who does not have a FACT-ES score measured at the 12 week time point. This is a conservative approach to imputation, as it will likely result in smaller differences between groups than would actually be present (if there is an actual difference), under the assumption that increased effects will occur over time up to week 12. In addition, a per protocol analysis of the primary outcome measure will be conducted,

which will include only those patients who follow the intervention as prescribed in the protocol, and who complete both the baseline and 12 week FACT-ES score.

Analysis of primary and secondary outcomes: Dichotomous outcomes will be summarized according to proportions and 95% confidence intervals. Continuous outcomes will be summarized according to means and standard deviations or medians and interquartile ranges as appropriate. The primary analysis will be based on a logistic regression analysis with adjustment for stratification factors. Additional logistic and linear regression analyses will be performed with adjustment for stratum. Univariable comparisons between the intervention and control groups will be examined using a Chi-Squared test for dichotomous events, and a student's t-test for continuous measures. Non-parametric methods may be used in lieu of these tests as appropriate. All analyses will be supplemented with 95% confidence intervals where relevant.

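### Section 5.2 names only single-visit methods for the repeated FACT-ES and FACT-B scores; a repeated-measures model would use partial follow-up at almost no cost, with a modest gain in precision

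*Combined protocol and SAP*

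**What the plan says.** Section 2.2 makes two multi-item scales secondary outcomes at four follow-up times. The first is the change in total score and individual items of "FACT-ES from baseline to 4, 8, 12 and 52 weeks following the beginning of endocrine therapy". The second is the change in FACT-B total and subscales at the same times. Section 3 and the study calendar schedule the questionnaires at baseline and at all four follow-up visits.

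The methods are in section 5.2. Two-group comparisons are to be "examined using a Chi-Squared test for dichotomous events", and the same sentence gives Student's t-test for continuous measures. It is preceded by: "Additional logistic and linear regression analyses will be performed with adjustment for stratum". Non-parametric substitutes are allowed but not named. The documents mention no mixed model, GEE, repeated-measures analysis, arm-by-visit term or summary over visits.

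Section 5.2 carries the last observation forward for patients lost to follow-up or without a 12-week FACT-ES score. The justification given is an expectation that effects increase up to week 12. The section does not say whether this rule also applies to the secondary outcomes or to week 52.

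**The concern.** Each patient can give four correlated follow-up scores per scale. A t-test or an ordinary linear regression of the change to a given week uses one of them. Two things are then at stake.

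- **Missing visits.** Questionnaires are completed mainly through an emailed link and no study visit is required, so some will be missed. In an available-case comparison at week 52, a patient with only weeks 4 and 8 contributes nothing. If the only adjustment is for stratum, the comparison is unbiased only when missingness is unrelated to earlier scores, given arm and stratum. Patients with worse early symptoms may well be those who stop responding.
- **Precision.** The earlier scores predict the missing later ones, and that information is not used.

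The point concerns the FACT-ES total, the FACT-B total and the FACT-B subscales as continuous secondary outcomes. It does not concern the primary analysis.

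**Working it through.** **The plan's own figure.** The inputs in 5.1 are "40% with a clinically meaningful change in one arm and 60% in the other", two-sided alpha 0.05 and 80% power. Without continuity correction:

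n = [1.96·√(2·0.5·0.5) + 0.8416·√(0.4·0.6 + 0.6·0.4)]² / 0.2² = (1.386 + 0.583)² / 0.04 ≈ 96.9 per arm, which is 97 per arm or 194 in total.

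With continuity correction:

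n′ = (96.9/4)·[1 + √(1 + 4/(96.9·0.2))]² ≈ 106.7, which is 107 per arm or 214 in total.

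This matches "we would need 214 total patients to achieve 80% statistical power". Exact enumeration of Fisher's test at 107 per arm gives 79.5% power. The inflation is 214 × 1.10 = 235.4, matching 235. None of this depends on how the secondary scores are modelled.

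**Gain at a given visit.** The documents give neither a within-patient correlation nor a missing-data rate by visit, so these are assumed:

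- equal correlation ρ between any two follow-up scores, 0.5 to 0.8;
- equal variance at each visit;
- monotone dropout, in two scenarios. In A, 10% are missing at week 12 and 20% at week 52. In B, 5% and 10% are missing.

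For dropout pattern k (fraction f_k, with S_k selecting the observed visits and C the correlation matrix), the information on the four arm differences is

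I = Σ f_k · S_k′ (S_k C S_k′)⁻¹ S_k.

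The model-based variances are the diagonal of I⁻¹. The available-case variance at a visit is 1/(fraction observed). The ratio of the two is the quantity of interest.

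At week 12 this reduces to

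ratio = 1 − m·R², where m is the fraction missing and R² = 2ρ²/(1+ρ) comes from predicting week 12 from weeks 4 and 8.

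- ρ = 0.5: R² = 0.333, so scenario A gives 1 − 0.1·0.333 = 0.967.
- ρ = 0.8: R² = 0.711, so scenario A gives 1 − 0.1·0.711 = 0.929.

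The week-52 values come from the full matrix:

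| Scenario | Visit | Ratio, ρ = 0.5 | Ratio, ρ = 0.8 | Variance reduction | CI narrower by |
|---|---|---|---|---|---|
| A (10%/20%) | 12 | 0.967 | 0.929 | 3–7% | 2–4% |
| A | 52 | 0.929 | 0.855 | 7–15% | 4–8% |
| B (5%/10%) | 12 | 0.983 | 0.964 | 2–4% | 1–2% |
| B | 52 | 0.965 | 0.927 | 4–7% | 2–4% |

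The CI column is 1 − √ratio. With complete data the gain at a single visit is close to nil.

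**An average over visits.** In scenario A, the variance of the mean arm difference over weeks 4, 8 and 12, relative to the available-case week-12 difference, is 0.607 (ρ = 0.5) to 0.783 (ρ = 0.8). If the effect were the same at all three visits, that would equal 1/0.783 to 1/0.607, or 28–65% more patients. If it is not,

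relative efficiency = (mean effect / week-12 effect)² / variance ratio.

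- Effects rising 1/3, 2/3, 1: the mean is 0.667, so 0.444/0.783 to 0.444/0.607 = 0.57 to 0.73.
- Effects rising 0.5, 0.75, 1: the mean is 0.75, so 0.5625/0.783 to 0.5625/0.607 = 0.72 to 0.93.
- Break-even is a mean effect of √0.607 to √0.783, or 0.78 to 0.88 of the week-12 effect.

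The average therefore has less power than week 12 alone under either rising pattern.

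**The case against.** Several objections have force.

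- **The plan never says that visits are compared one at a time.** This stands. It is an inference from the outcome definitions in 2.2 and the methods in 5.2, and the regression sentence leaves the data structure open. The fair charge is that the plan names only single-visit methods and no repeated-measures model.
- **The like-for-like gain is small.** This stands too. The 20% loss at week 52 is an assumption; the documents' only allowance is the 10% inflation in 5.1, which also covers stratification. Scenario B shows the smaller gain.
- **The comparator may differ.** If last observation carried forward also applies to the secondary outcomes, the available-case comparison does not describe the plan's analysis. The scope is unclear, which is itself a reason to settle it. The reason given for the rule speaks only of effects up to week 12 and offers nothing for week 52.
- **These outcomes are supportive.** Section 5.2 says so under compliance and loss to follow-up. A reader might infer that the secondary FACT results will carry most of the trial's interpretation; the documents say the opposite.

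A reader might also infer that a longitudinal model is worth 28–65% more patients, or that the average over weeks 4 to 12 should be the single summary. The documents do not support either. That figure compares two different estimands and needs a constant effect, while 5.2 expects effects to grow up to week 12.

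A repeated-measures model that reports four visit differences does not remove the multiplicity of four looks per scale.

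**Conclusion.** The point holds in a limited form. For the continuous secondary FACT outcomes, the methods named in 5.2 imply separate comparisons at each visit and leave the correlation between visits unused. The main benefit of a repeated-measures model is validity under missing-at-random with partial follow-up included. The precision benefit is secondary: a 3–7% lower variance at week 12 and 7–15% at week 52 in scenario A, and about half that in scenario B. These figures rest on assumed equal correlations and variances, assumed dropout rates and an available-case comparator. This is a cheap improvement, not a flaw in the trial's main result.

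**What to change.** In section 5.2, for FACT-ES total, FACT-B total and each FACT-B subscale, replace the t-tests with one mixed model for repeated measures per scale:

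- all observed scores at 4, 8, 12 and 52 weeks;
- arm, visit, arm-by-visit, baseline score, baseline-by-visit and the stratification factors;
- unstructured covariance;
- a statement that values are not carried forward for these outcomes.

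Report the arm difference with 95% CI at each visit. An average over visits may be added as a supplementary estimate, labelled as a different estimand that gains power only if the effect is roughly constant over visits. Leave the primary analysis as it is.

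The cost is a change of wording before analysis and slightly more programming. No further data, visits or patients are needed.

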5.3 Randomization and Stratification

Eligible and consented patients will be randomized using a permuted block design developed by the Ottawa Methods Centre to receive either one of the two study arms (1:1). The variable block sizes will be randomly selected between sizes of 4 and 6. Subjects will be stratified based on: study site, tamoxifen (yes/no), and chemotherapy (yes/no). The patient will be randomized through a secure web-based randomization system on the physician's clinic desktop or mobile device or through the designated study CRA. The randomization system also confirms the study eligibility criteria prior to randomization. The study does not involve changing the standard of care patients receive.

The study co-investigators (i.e. study qualified physicians) will ensure verbal consent and eligibility review has taken place prior to randomization. For all patients, the primary oncologist will dictate in the patient's electronic medical record that the consent process has taken place.

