Chronotherapy, also called chronotherapeutics, is defined as the administration of a medication in coordination with the circadian rhythm in order to minimize side effects and yield a greater efficacy¹⁵. While this concept is based on a strong mechanistic foundation involving xenobiotic metabolism and detoxification of drugs, only a few clinical trials, mainly for neurologic, behavioral and psychiatric conditions, factored in circadian timing¹⁵. Recently, a study demonstrated that the time of day at which antihypertensives are taken can impact their effectiveness¹⁶. In breast cancer, one randomized trial evaluating the optimal time for administering vinorelbine showed a non-statistical benefit for the incidence of grade 3-4 neutropenia when administered at 21:00 and grade 3-4 gastrointestinal toxicity when administered at 10:30¹⁷. Furthermore, there is some evidence suggesting that the adherence to drugs might be greater in the morning as compared to the evening¹⁸. Many online forums exist with breast cancer patients seeking insight on the time of day (i.e. morning vs evening) to take their endocrine therapy¹⁹. In

our practice, we often see doctors and nurses using a trial and error method to help patients determine the best time of day at which to take their endocrine therapy to try reducing these side effects, with anecdotal success. Even though this clinical practice is not evidence-based, there is increasing molecular evidence suggesting an interplay between circulating estradiol and expression of circadian clock genes that may support this practice²⁰.

Evidence from a recent systematic review

Our team recently conducted a systematic review to assess the evidence currently available regarding the circadian administration of endocrine therapy in terms of side effects, quality of life and disease-free survival in breast cancer patients. Ovid Medline, EMBASE, and the Cochrane Central Register of Controlled Trials were searched from 1947 to August 2020 for relevant randomized control trials or prospective cohort studies and off 361 unique citations identified, 0 studies met eligibility criteria.

Ongoing clinical trials

A search of the ClinicalTrials.gov database to identify all active registered trials looking at the best “time-of-day” administration of endocrine therapy was done on December 18, 2020. No registered studies on this specific question were found.

Clinical trial rationale

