5.4 Blinding

Patients and investigators will not be blinded to treatment allocation as the study is randomizing treatment schedule only. This is in keeping with a pragmatic trial design

6. *TIMELINE AND FOLLOW-UP*

We would anticipate that the study will take two years for accrual and 1 year for completion of follow-up on the quality of life primary study endpoint. Therefore, we would anticipate that the study runs for 2.5 years.

7. *DATA COLLECTION*

Once the patient has been randomized, the study CRA will collect participant information on patient demographics (e.g. age), tumour characteristics (e.g. stage), surgery type, chemotherapy use, radiotherapy use and endocrine therapy type. From a study standpoint only the CRA will access this information. Data not available at the time of visit will be collected from the dictated physician note. CRAs will enter data into the electronic database developed by the Ottawa Methods Centre within the timeframes agreed in the site agreement.

The physician will document any study related events either in his dictated physician note and will complete a Health Care Provider Questionnaire at the 12 week clinic visit and at 52 weeks (end of study). This questionnaire will collect study related events including:

compliance to dose timing (date at which patient decided to change dose time and reasons), discontinuation of endocrine therapy (date and reasons), switch from an endocrine therapy type to another one (date and type and reasons). To reflect real-world practice, no additional clinic visit will be required, but participants will be contacted by a CRA or a health care provider at 12 weeks and 52 weeks to collect compliance information. In addition, treating physicians are encouraged to email the CRA if at any time a significant event (i.e. hospitalization, recurrence or death) occurs.

Participant data to be collected over the treatment period:

- Treatment assignment
- Treatment received
- FACT-ES questionnaire for assessing endocrine therapy symptoms and FACT-B questionnaire for assessing quality of life. Because the first portion of the FACT-ES and FACT-B questionnaires are the same, we will only have study participants complete the duplicate sections once at each time point (combined into FACT-B and ES questionnaire)

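### Section 5.3 prints both block sizes in an open-label trial stratified by site, so someone who has followed a stratum can deduce some upcoming allocations

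*Combined protocol and SAP*

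**What the plan says.** Section 5.3 specifies 1:1 permuted-block randomization, stratified by study site, tamoxifen use and chemotherapy use. On the blocks it says: "The variable block sizes will be randomly selected between sizes of 4 and 6". The allocation is obtained through a "secure web-based randomization system on the physician's clinic desktop or mobile device or through the designated study CRA", after consent and an eligibility check. The same section describes the enrolling physicians as study co-investigators.

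Section 5.4 says: "Patients and investigators will not be blinded to treatment allocation". Sections 3 and 3.1 have the treating medical oncologist approach patients at routine visits. The Background describes "doctors and nurses using a trial and error method to help patients determine the best time of day".

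Nothing in the documents keeps the block sizes in a separate restricted file or limits who at a site may see earlier allocations. Nor do they say who does see them.

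**The concern.** Allocation concealment depends on the recruiter being unable to foresee the next assignment. A central web system hides the list, but it cannot stop someone from working out the end of a block when three things are known: the possible block sizes, the stratum, and the earlier allocations in that stratum. Section 5.3 supplies the first. The second is usually known in clinic, because tamoxifen and chemotherapy are treatment decisions. The third is open to anyone who has kept track, because the trial is unblinded.

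If a patient were approached, deferred or passed over because of a foreseen arm, the arms could differ in ways nobody measured. The primary outcome is a patient-reported score (section 2.1), and the planned adjustment for stratification factors (section 5.2) would not remove such a difference.

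**Working it through.** **Plan's own figures.** The plan gives no predictability figure. Its sample size is not affected: 40% versus 60%, two-sided alpha 0.05 and 80% power give 214 with a continuity-corrected formula, and 214 x 1.10 = 235.4, stated as 235.

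**Inputs from the documents.** Block sizes 4 and 6, ratio 1:1, strata of site x tamoxifen x chemotherapy (2 x 2 = 4 per site), target 235.

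**Assumptions.** Both block sizes equally likely (odds not stated). The observer knows all earlier allocations in the stratum. Strata are equal in size. The trial has 2 to 15 sites: the number is not stated, and 15 is the centre count that section 1.1 gives for the wider programme.

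**Step 1: two alike at the start of a block.** P(two alike) is 1/3 for size 4 and 2/5 for size 6. The posterior for size 4 is (1/3)/(1/3 + 2/5) = 0.4545. The next allocation is the other arm with probability 0.4545 x 1 + 0.5455 x 0.75 = 0.864.

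**Step 2: a 2:1 split after three.** Its probability is 1 for size 4 and 0.9 for size 6, so the posterior for size 4 is 1/1.9 = 0.526. The fourth goes to the under-represented arm with probability 0.526 x 1 + 0.474 x 2/3 = 0.84.

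**Step 3: certain allocations in the first block of a stratum.**
- Position 4 is certain after three alike, which rules out size 4: 0.5 x 0.1 = 5%.
- Positions 5 and 6 are certain after a 3:1 split in four: 0.5 x 0.4 = 20% each.
- Average over four positions: 0.05/4 = 1.3%. Average over six: (0.05 + 0.20 + 0.20)/6 = 7.5%.

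**Step 4: whole strata** (exact enumeration to 14 positions, simulation beyond).

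| Sites (assumed) | Mean stratum, 235/(4 x sites) | Certain | Of 235 | Stratum with at least one certain |
|---|---|---|---|---|
| 2 | 29 | 5.7% | 13 | 51% |
| 5 | 12 | 6.3% | 15 | 30% |
| 10 | 6 | 7.5% | 18 | 19% |
| 15 | 4 | 1.3% | 3 | 5% |

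The share predictable with at least 80% probability is about 34% in strata of 4, 27% in strata of 8, 30% in strata of 12 and 29% in strata of 20.

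**Step 5: what disclosure adds.** The table compares correct guesses by an observer who knows the sizes with those from simply guessing the under-represented arm.

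| Stratum size | Sizes known | Simple counting |
|---|---|---|
| 4 | 65.4% | 65.3% |
| 8 | 66.8% | 66.8% |
| 12 | 67.9% | 68.2% |
| 20 | 68.6% | 68.5% |
| 29 | 68.4% | 68.4% |

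The differences are simulation noise. Knowing the sizes adds certainty in particular cases, not a better average guess.

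**Step 6: adding a longer block.** With sizes 4, 6 and 8, even if all are known, certain allocations in strata of 12 fall from 6.1% to 2.4%, and those at least 80% predictable fall from 30% to 17%. In strata of 4 the latter fall from 34% to 2%. The average guess rate falls by about 0.5 to 3 points.

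**The case against.** The case against giving this much weight is substantial, and most of it stands.

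- **Access to the history.** A reader might infer that every enrolling physician sees every allocation at the site. The documents do not say so. Physicians may randomize on their own devices, and section 7 restricts study access to patients' chemotherapy and endocrine therapy data to the CRA. A CRA or a lone enroller could follow a stratum; several oncologists sharing a site are not shown to be able to. The CRA, who is best placed to predict, is not the person whom sections 3 and 3.1 name as approaching patients. That physicians hold the protocol is itself inferred from their co-investigator role.
- **Stratum size.** Without the number of sites, it is not established that strata are small. At 15 sites only about 3 allocations would be certain.
- **Motive.** A reader might take the account of clinicians trying different times of day as a reason to steer patients. It names no favoured arm, and section 1.1 asserts equipoise.
- **Existing safeguards.** Randomization is central and web-based, consent and eligibility come first, and the sizes vary. A known fixed block of 4 would make (1/3 + 1)/4 = one third of allocations certain.
- **Size of any bias.** Suppose, purely as an illustration, that all of a 6% certain share were exploited and those patients' response rates differed by 20 points between arms. The bias would be 0.06 x 20 = 1.2 points, against a design difference of 20.

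What remains is that the sizes are in the protocol, that some allocations then follow with certainty for anyone who has the history, and that the documents contain nothing to prevent it.

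**Conclusion.** The point holds as a minor weakness in allocation concealment. The shares in the working rest on equal odds of the two sizes and a fully tracked stratum; the counts out of 235 also rest on an assumed number of equally filled sites.

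Two stronger readings are not supported. The first is that hiding the sizes would make allocation unpredictable: most of the predictability comes from short blocks within strata and survives non-disclosure. The second is that the trial's result is or will be biased: the documents show neither a preference for one arm nor any steering. The change is worth making because printing the sizes has no evident benefit for the sites and removing them costs little.

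**What to change.** 1. Delete the block sizes from section 5.3 and from any site-facing document. Hold them in a restricted randomization file at the Ottawa Methods Centre.
2. In section 5.3 state only: *permuted blocks of randomly varying, undisclosed size*.
3. Include a longer block in the schedule, or in its unused part if accrual has begun (the documents do not show whether it has). This matters because staff who have read the present sizes cannot unlearn them, and because the longer block is what lowers predictability rather than only the observer's confidence.

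The cost is one sentence and a revised list, plus slightly more arm imbalance in strata that end mid-block. The sample size and the analysis do not change.
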